Specific Aim 2: To examine the long-term effect of intermittent (1 hour daily) LLTS on inflammatory cytokines, including tumor necrosis factor (TNF)- α and interleukin (IL)-6, as well as their gene expression, in patients with paroxysmal AF over a 6-month period. The importance of this aim is highlighted by accumulating evidence for a role of inflammatory mechanisms in AF. Blood samples will be collected from patients at baseline, and at 3 and 6 months. These cytokines will be measured using multiplex immunoassays. Gene expression of these inflammatory cytokines will be measured from peripheral blood monocytes, using commercially available microarrays. All the tests in Specific Aim 2 will be conducted at the laboratory of [name] (collaborator).

B. Background and significance

Atrial fibrillation is the most common clinically significant cardiac arrhythmia and is associated with increased cardiovascular morbidity and mortality ^{1,2}. Both the incidence and prevalence of AF increase with age ^{3,4} and based on a recent estimate, the number of patients with AF in the US is expected to reach 15 million by 2050, as the population ages ⁵. The total incremental cost of AF is estimated to be approximately \$8,700 per patient per year, driven primarily by the increased rate of hospitalizations, while treating patients with AF costs an additional \$26 billion per year to the US healthcare bill ⁶. Despite these alarming numbers, the therapeutic success of currently available strategies for treating AF (antiarrhythmic medications and catheter ablation) is far from being optimal ⁷. Specifically, the long-term efficacy of catheter ablation for AF, as reported recently by 2 very experienced centers, has been disappointing, ranging from 29% to 46% at 5 years after a single procedure ^{8,9}. Catheter ablation, with the poor long-term success rate and high cost, is not likely to be the mainstay therapy for a large population of patients with drug-refractory AF. The development of alternative non-pharmacological, non-ablative therapies is essential for the management of patients with AF.

Neuromodulation is a novel therapy that has been successfully used in a variety of diseases. Vagus nerve stimulation delivered through an implantable device is being frequently used for the treatment of drug-refractory epilepsy ^{10,11}. Preliminary studies of the use of VN stimulation through an implantable device in patients with heart failure showed promising results, including

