Based on the observation that transcutaneous electrical stimulation of the tragus, the anterior protuberance of the outer ear, where the auricular branch of the vagus nerve is located, elicits evoked potentials in the brainstem in humans ²⁸, we examined the effects of low-level tragus stimulation (LLTS) for inhibiting AF in a canine model of rapid atrial pacing ²⁹. Notably, the antiarrhythmic effects of LLTS were similar to those of LLVNS delivered to the cervical vagus nerve trunk ²⁹. We recently translated these results into patients with drug-refractory AF undergoing AF ablation, and showed that LLTS for just one hour significantly shortened the AF duration, and suppressed inflammatory cytokines, indicating that neuromodulation by LLTS is a very promising, non-invasive therapy to treat AF and AF-related inflammation ³⁰. Before these results can be translated into clinical practice, the long-term clinical efficacy of this approach needs to be shown in ambulatory patients with AF. It has been recently shown that transcutaneous VN stimulation applied for just 15 minutes in healthy volunteers increases heart rate variability (HRV) and reduces sympathetic nerve activity ³¹. In this study, we hypothesize that intermittent (1 hour daily) LLTS for 6 months may decrease AF burden and suppress inflammatory cytokines in patients with paroxysmal AF. These investigations will establish the first evidence of the long-term effects of LLTS on AF suppression in patients with paroxysmal AF and may provide the basis for a potential expansion of the therapeutic targets of this treatment modality beyond AF, into other inflammatory conditions, including atherosclerosis ³².

C. Preliminary studies

IRB NUMBER: 5631
IRB APPROVAL DATE: 07/10/2017

LLTS suppresses AF in dogs: We studied the effects of transcutaneous electrical stimulation at the tragus for inhibiting AF. In 10 pentobarbital-anesthetized dogs, LLTS (20 Hz) in the right ear

[figure not shown]
[figure not shown]

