Active LLTS will be performed by use of a transcutaneous vagus nerve stimulation (tVNS) device with electrodes attached to the tragus of the ear, which is innervated by auricular branch of the vagus nerve ³⁵.

The Parasym targeted transcutaneous vagus nerve stimulation (tVNS) device (Parasym Ltd) will be used for LLTS or sham stimulation. The device will be connected to a clip electrode that will be attached to the external ear. In the active group, the ear clip electrode will be attached to tragus in the active stimulation group (Figure 3). The ear (tVNS) device has not been previously reviewed by the FDA for experimental studies. It has been however studied in Europe and is available in the European market under the name Parasym ®. The same LLTS protocol will be followed in sham LLTS arm, but the electrode will be placed on the ear lobe, which is devoid of vagus innervation 35. The LLTS unit will be set at a pulse width of 200 µs

[figure not shown]
Figure 3. Position of the electrode clip used for active stimulation on the tragus.

and a pulse frequency of 20 Hz. Amplitude will be titrated to the level of sensory threshold, typically in the range of 10-50 mA. The stimulation strength will be gradually increased until the patient experiences mild discomfort, then decreased by 1 mA below that threshold. LLTS will be applied continuously for 1 hour daily. After individual training, participants will apply LLTS by themselves as part of their daily routine. Participants will be requested to keep a daily log with the time and duration of LLTS application, amplitude settings and any comments related to each daily session to monitor adherence. Patients and investigators will be blinded to the treatment allocation. Blinding of the patients will be accomplished by having a sham control arm, in which stimulation will be delivered to a different site (the ear lobe), devoid of vagal innervation ³⁵. Thus, all patients will be aware that they are receiving stimulation, but they will not be told which site achieves active stimulation. The clinical coordinator will be unblinded to treatment allocation and will instruct the patients on the proper use of the device. In patients with pacemakers, the pacemaker will be

tested with the LLTS unit to assess for interaction. In case of interaction (the stimulation artifact of the LLTS unit picked up by the pacemaker), the patients will be excluded from the study.

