Patients will be anticoagulated according to the 2014 ACC/AHA guidelines ³⁶. Specifically, patients with a CHADS2-VASc score of 1 or greater will receive anticoagulation, with either one of the new oral anticoagulants or warfarin (target INR 2-3). All other medications, including antiarrhythmic medications will be continued. The choice of antiarrhythmic medications will be left at the discretion of the treating physician. The experimental device will be used in addition to all the other medications; in other words, the device will be used only with individuals continuing drug treatment.

Patients will be enrolled in the study over 17 months and the total duration of the study will be 24 months (each patient will be followed for 7 months). During the baseline visit (after the 2 week monitoring period), a complete history and physical examination will be done by one of the investigators. Laboratory data and echocardiographic data, when available, will also be reviewed. A 5-minute ECG for HRV analysis (see below) will be performed at the same time. After the ECG is completed, 10ml of blood will be drawn for cytokine analysis (see below). Since blood draw is likely to cause an increase in the sympathetic tone, it will be performed after the ECG is completed, to avoid any interfering with HRV analysis. After the ECG and blood draw is completed (to avoid

contamination of the baseline data by stimulation), patients will be instructed on how to use the LLTS and attach the electrode pads and will be asked to repeat the process themselves under direct supervision, to ensure correct use of the device. This process will be done by a clinical coordinator and/or physician who is unblinded to random allocation.

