We intend to recruit 52 patients. Participants will be evaluated at 1, 3 and 6 months. At each follow-up visit, patients will have a brief history and physical examination, and any cardiovascular events, including symptomatic AF episodes will be recorded. In addition, the discomfort threshold for tragus stimulation will be obtained to ensure that patients are receiving adequate stimulation. At the 1 month visit, the patients will be interviewed by the unblinded physician or clinical coordinator to address any issues with LLTS administration at home, and to assess their adherence to the stimulation protocol. At the 3 and 6 month visit, patients will have a 5-minute ECG and blood drawn, as during the baseline visit. In addition, patients will undergo noninvasive continuous ECG monitoring for 2 weeks to evaluate their AF burden using an adhesive patch (Zio[®] Patch).

A schematic representation of the study design and timeline of events is shown in Figure 4.

HRV analysis: HRV is a marker of VN activity and can be easily measured by software calculating the distance between consecutive R waves on the ECG ³⁷. Importantly, measures of HRV have been inversely correlated with inflammatory cytokines (C-reactive protein, IL-6) in the general population ³⁸⁻⁴⁰. At each visit, a 5-minute ECG will be obtained for HRV analysis. ECG will be obtained in the supine position after resting for 15 minutes while heart rate, blood pressure and respiration will be monitored. All participants will be asked to avoid caffeine for 4 hours and alcohol, smoking and exercise for 12 hours prior to the visit to avoid any interfering with the results of their ECG. This test will done using a PC-Based ECG device. Analysis and interpretation of the HRV data will be performed in a blinded fashion.

Specific Aim 2: To examine the effect of intermittent (1 hour daily) LLTS on inflammatory cytokines and their gene expression in patients with paroxysmal AF over a 6-month period.

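### HRV recordings and blood draws at 3 and 6 months are not separated from a home session earlier that day, so these secondary outcomes may mix an acute effect with the long-term effect of Aim 2

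*Combined protocol and SAP*

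**What the plan says.** Specific Aim 2 in Section A is "To examine the long-term effect of intermittent (1 hour daily) LLTS on inflammatory cytokines" and on their gene expression. Section E lists HRV measures and serum cytokine levels as secondary outcomes.

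Section D protects the baseline measurements. The ECG comes first, then the blood draw, and only then the device training, the stated reason being to avoid "contamination of the baseline data by stimulation".

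For follow-up, Section D says: "At the 3 and 6 month visit, patients will have a 5-minute ECG and blood drawn, as during the baseline visit". It also has the discomfort threshold obtained at each follow-up visit, without giving its order relative to the ECG and blood draw. The HRV paragraph sets the pre-visit restrictions: "All participants will be asked to avoid caffeine for 4 hours and alcohol, smoking and exercise for 12 hours prior to the visit". Stimulation is not among them.

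At home, "participants will apply LLTS by themselves as part of their daily routine", for one hour a day with no clock time set. Patients log the time, duration and amplitude of each session so that adherence can be monitored.

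On acute effects, Section B reports that "transcutaneous VN stimulation applied for just 15 minutes in healthy volunteers increases heart rate variability (HRV") and that "LLTS for just one hour significantly shortened the AF duration, and suppressed inflammatory cytokines". The model in Section E has terms for group, time, group by time and the baseline measure. It has none for time since the last session.

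**The concern.** Section D accepts that stimulation shortly before sampling can contaminate HRV and cytokine data, and guards the baseline against it. At follow-up the same measurements are taken from patients who own the device and may have used it an hour earlier or the day before. The sham site is described as devoid of vagal innervation, so on the protocol's own reasoning any acute shift falls in the active arm only.

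The interpretation of Aim 2 is what is at stake. The trial is meant to move from acute suppression, already reported in the earlier randomised study in ablation patients, to long-term effects. A between-arm difference in HRV or TNF-α at 6 months could partly repeat that one-hour effect, and the data as planned could not tell the two apart. Uneven time since the last session would also add variation within the active arm. The exploratory analyses that define cytokine response as a decrease at 6 months would inherit it.

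**Working it through.** **What is covered and what is not**

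| Source of stimulation before sampling | Baseline | 3 and 6 months |
|---|---|---|
| Device handling in clinic | Placed after ECG and blood | Plausibly the same, through the reference back to the baseline visit |
| Discomfort-threshold test | Not applicable before ECG and blood | Done at each follow-up visit; order not stated |
| Home session earlier that day | Impossible, no device yet | Not covered |

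The reference back to baseline cannot cover the last row, because at baseline there was no home session to exclude. The model does not repair this. Adjusting for a stimulation-free baseline leaves an acute shift at follow-up in place, and so does pooling the 3- and 6-month data when the interaction is not significant.

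**The plan's own figure.** The only power statement concerns AF burden: a difference of 28.4 − 3.7 = 24.7 points, SD 31.2 and 26 per group. With the noncentral t distribution this gives 79.9% power, in line with the stated 80%. It does not bear on HRV or cytokines; only the 26 per group is used below.

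**How often a same-day session could precede the visit.** The documents give no clock times. Assume session start S uniform on 07:00–21:00 and visit time V uniform on 09:00–16:00. The session then ends at E = S + 1, uniform on 08:00–22:00, a 14-hour range.

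- Same-day session already finished: (mean of V − 8)/14 = (12.5 − 8)/14 = 0.32. Expected number in the active arm: 0.32 × 26 ≈ 8.
- Finished within the previous 4 hours: average of min(V − 8, 4)/14 over the 7 visit hours = (7.5 + 16)/(7 × 14) = 0.24.
- Usual session hour overlapping the visit: 1/14 = 0.07.
- Hours since the last completed session: 5th percentile 0.7, median 16.9, 95th percentile 23.3.

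The range over other assumptions is wide. If every patient used the device after 16:00, the share would be 0%. If every patient finished before 09:00, it would be 100%.

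**What an acute shift could do to the comparison.** The documents give no SD, acute effect size or carry-over time for these outcomes at follow-up, so this too is an illustration. Suppose there is no other effect. A share p of active patients is sampled while an acute shift of a SD is present, there are 26 per arm, one visit, and two-sided α = 0.05. The mean difference is m = p·a, the pooled SD is √[(2 + p(1 − p)a²)/2], the SE is SD·√(2/26), and the chance of significance is Φ(m/SE − 1.96) + Φ(−m/SE − 1.96).

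For a = 0.5 and p = 0.5: m = 0.25, SD = 1.016, SE = 0.282, m/SE = 0.89, chance 14.4%.

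| Acute shift | p = 0 | p = 25% | p = 50% | p = 100% |
|---|---|---|---|---|
| 0.3 SD | 5% | 5.8% | 8.4% | 19.1% |
| 0.5 SD | 5% | 7.3% | 14.4% | 43.8% |
| 0.8 SD | 5% | 10.8% | 28.4% | 82.2% |

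If the acute effect lasted about 4 hours, the timing scenario (24%) would sit near the 25% column.

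**The case against.** The strongest reply is that the daily hour is the treatment, so its recurring effect belongs to what is being compared. Baseline data must be treatment-free; follow-up data need not be. Section D restates Aim 2 as the effect of daily LLTS over a 6-month period, and no off-treatment persistence is claimed. This largely stands: the comparison with sham is a valid randomised estimate of the effect of being on the regimen. It does not settle the point, because Section A words Aim 2 as a long-term effect and the benefit section promises first evidence of long-term effects on inflammation.

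The acute evidence is also narrower than it first looks. The 15-minute HRV result is from healthy volunteers. The one-hour cytokine result is from anaesthetised ablation patients, for TNF-α and CRP in femoral-vein but not coronary-sinus samples. No acute result is reported for IL-6 or gene expression, and no duration of effect is given. On the timing scenario above, about 68% of visits fall at least 11 hours after the last completed session. Figure 4 could not be read in the text version and could hold a timing detail, though no sentence points to one.

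A reader might infer that the follow-up results are contaminated, or that nothing at all guards the follow-up measurements. The documents support neither reading. Contamination depends on visit-day habits and on how long the effect lasts, and neither is stated. The reference back to the baseline visit plausibly carries over the in-clinic order. Nor are 8 of 26 patients a ceiling: that is an expected count under one assumed scenario.

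**Conclusion.** The gap is real, and its reach is limited. As written, the plan allows HRV and cytokines at 3 and 6 months to be measured soon after a home session or after the threshold test, with no record of the interval in the analysis. A difference on these outcomes may therefore combine an acute effect with the long-term effect that Aim 2 seeks.

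The size cannot be fixed from the documents. About a third of visits following a same-day session rests on the assumed uniform times, and any inflation of false long-term findings rests on an assumed shift and carry-over.

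Only secondary outcomes and the related exploratory analyses are touched. A reader might infer that the main result is undermined too. It is not: this point does not reach the primary outcome, AF burden over a 2-week recording, or the sample size. The plan should be changed because the remedy is nearly free and the protocol already applies its principle at baseline.

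**What to change.** 1. In the follow-up paragraph of Section D, extend the baseline principle to the 3- and 6-month visits: the 5-minute ECG and the blood draw are taken before that day's stimulation, including the discomfort-threshold test, with the daily hour otherwise unchanged. Any minimum interval is for the investigators to set.
2. Derive hours since the last session at each of these visits from the daily log, in both arms.
3. In Section E, prespecify a sensitivity analysis of HRV and cytokines by that interval.

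The cost is one sentence in the visit instructions, one derived variable and one extra analysis, with no added patients, visits or samples. Some patients or visits must shift their timing on two days.

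The change does not make the interval uniform. On the same assumed times it would still run from 24 + 9 − 22 = 11 hours to 24 + 16 − 8 = 32 hours after the previous day's session. Any remaining difference should therefore be reported as the effect while on daily treatment, measured before that day's session.

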The primary outcome of this study is the percent of time spent in AF over the monitoring period (AF burden) at the 6-month time point. Secondary outcomes include total duration of AF over the 2-week monitoring period, longest daily duration of AF, measures of HRV and serum cytokine levels. Outcomes will be compared between groups using a Generalized Estimating Equations modeling approach, with 3 time points (baseline, 3 months, 6 months) and 4 terms included in the model (group effect, time effect, group by time interaction, adjustment for baseline measure).

Significant interactions will be followed by time trend analyses stratified by intervention group. If the interaction is not significant, the interaction term will be dropped from the model and the between-group comparisons will be made by combining the 3-month and 6-month data. For all pair-wise testing, we will adjust for multiple comparisons using Tukey's method. The modeling assumptions will be evaluated by plotting the residuals by the predicted values (for the constant variance assumption) and comparing the normal QQ plot with the QQ plot of the residuals (for the normality assumption). If the modeling assumptions are not satisfied, we will perform a natural log transformation of the data, to better satisfy these assumptions. For 0 values, a value of 0.01 will be added to each measure before applying the natural log. Analyses will be based on the intention-to-treat principle. In post-hoc exploratory analyses, we will use logistic regression analysis to identify predictors of clinical and cytokine response to LLTS, defined as a decrease of AF burden and a decrease in cytokines at 6-month follow-up, respectively. Those variables that which are associated with response to LLTS in univariate analysis at p<0.1 will be entered into a multivariate logistic regression model, using a backward elimination method to identify the most parsimonious model. In light of the limited sample size, such analyses will be underpowered and will be considered hypothesis-generating only. Statistical significance will be declared at p<0.05.

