Sample size and power calculations: For purposes of sample size calculations we have simplified the analysis to focus on the AF burden at the 6-month time point between the 2 groups. Assuming a mean±standard deviation AF burden in the control group of $28.4\pm31.2\%$ ³⁴ and a 87% reduction in the LLTS group to 3.7% (assuming a common standard deviation of 31.2%), 26 patients per group would provide 80% power to detect the specified effect sizes at a two-sided significance α level of 0.05. Approximately 30 patients with paroxysmal AF are seen in our clinics each month. Assuming that 1 out of 4 eligible patients would agree to participate in the study, we should be able to enroll the required number of patients within the proposed 17 months, allowing for 6 months of additional follow up and a final month for data analysis.

F. Gender/Minority/Pediatric Inclusion for Research

Participants will be age 21 or older. Race, minority status and gender will not affect enrollment.

[figure not shown]
G. Human participants

The study population will include 52 male/female patients with paroxysmal AF, aged 21 or older, including all races. Since AF is extremely rare in patients less than 21 years old, this age limit is not expected to affect the overall results.

Inclusion Criteria:

- 1. Male and female patients older than 21 year old
- 2. Paroxysmal AF

Exclusion Criteria:

- 1. Left ventricular dysfunction (Left ventricular ejection fraction <40%)
- 2. Significant valvular disorder (i.e., prosthetic valve or hemodynamically relevant valvular diseases)
- 3. Recent (<6 months) stroke or myocardial infarction
- 4. Severe heart failure (NYHA IV)
- 5. Left atrial dilatation (>55mm)
- 6. Recurrent vaso-vagal syncopal episodes
- 7. Unilateral or bilateral vagotomy
- 8. Pregnancy or breast feeding
- 9. Sick sinus syndrome, 2nd or 3rd degree AV block, bifascicular block or prolonged (PR>300ms) 1st degree AV block.
- 2. Identify sources of research material in the form of specimens, records or data.

The research information will consist of the AF burden and serum inflammatory cytokines at each time point specified in the protocol (see Figure 4).

- 3. Describe plans for recruitment and consent procedures to be followed.
- a. Describe the location where consent is most likely to take place (will consent be obtained while an inpatient, in the ER/ICU, will consents be mailed with follow-up meeting to discuss the consent, etc.).

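### The GEE uses baseline both as a time point and as a covariate, and neither branch of its decision rule names the 6-month between-group test that is the primary outcome

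*Combined protocol and SAP*

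**What the plan says.** Section E defines the primary outcome as the percentage of time in AF "over the monitoring period (AF burden) at the 6-month time point". It compares arms with a GEE "with 3 time points (baseline, 3 months, 6 months) and 4 terms included in the model". Besides group and time, the terms are "group by time interaction, adjustment for baseline measure".

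The plan then branches on the interaction:

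- **Significant:** "Significant interactions will be followed by time trend analyses stratified by intervention group".
- **Not significant:** the interaction is dropped, and "the between-group comparisons will be made by combining the 3-month and 6-month data".

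A further sentence reads "For all pair-wise testing, we will adjust for multiple comparisons using Tukey's method". It does not list the pairs.

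The sample size paragraph of the same section says "we have simplified the analysis to focus on the AF burden at the 6-month time point between the 2 groups", and concludes that "26 patients per group would provide 80% power to detect the specified effect sizes". Section D (Research design and Methods) places the first two-week recording before randomization. The secondary outcomes use the same model.

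**The concern.** There are two separate problems.

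**What the interaction tests.** The branching rule makes sense only if the interaction asks whether the treatment effect differs between 3 and 6 months. If baseline rows are responses, it asks something else. The expected group difference is zero at baseline and non-zero afterwards, so even a perfectly stable effect is an interaction. A treatment that works as planned would then usually be sent down the branch meant for changing effects.

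**Which test is primary.** Trends within each arm do not compare the arms. The pooled comparison does, but it targets the average of 3 and 6 months, not the 6-month value. The Tukey sentence does not supply the missing contrast because it names no pairs.

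Randomized inference is not lost. The three-row interaction is itself a randomized comparison of change from baseline, and a 6-month contrast would be unbiased if reported. What is lost is a single pre-specified primary test and estimate. A reader cannot tell in advance whether the interaction, the pooled test or a Tukey-adjusted pair decides the trial.

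**Working it through.** **Inputs from the sample size paragraph.** Control mean 28.4, active mean 3.7, so d = 24.7; common SD σ = 31.2; n = 26 per arm; two-sided α = 0.05.

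**Assumed, because the documents do not give them.** Within-patient correlation r = 0.3, 0.5 or 0.7, equal between all visits; effect equal at 3 and 6 months unless stated; normal, complete data. Simulations used 4,000 trials per scenario, an independence GEE and robust standard errors.

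**1. The plan's own figure.** SE = 31.2 × √(2/26) = 8.65, and 24.7/8.65 = 2.85. Noncentral t power on 50 df is 79.9%. The stated 80% reproduces.

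**2. Interaction with baseline rows as responses.** With complete data the baseline covariate shifts all of a patient's rows equally, so it drops out. The 2-df contrast is the between-arm difference in the two changes from baseline. Its noncentrality is λ = n d² / [3σ²(1 − r)] = 26 × 24.7² / [3 × 31.2² × (1 − r)].

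| r | λ | Analytic (chi-square) | Simulated | Simulated, follow-up rows only |
|---|---|---|---|---|
| 0.3 | 7.76 | 70% | 66-74% | 4-7% |
| 0.5 | 10.86 | 85% | 82-87% | 4-7% |
| 0.7 | 18.11 | 98% | 96-98% | 4-7% |

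The simulated ranges cover a chi-square reference with uncorrected SEs, an F reference, Mancl-DeRouen SEs with F, and linear time. At half the effect the figures fall to 19-25%, 26-34% and 43-50%. There most trials (about half at r = 0.7) would reach the pooled comparison instead.

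**3. False positives if either branch counts as success.** Under the null, the three-row interaction alone rejects in about 4-8% of trials. Either a significant interaction or a significant pooled test occurs in 10-12% with uncorrected robust SEs, 9-10% with an F reference, and 7-8% with small-sample-corrected SEs.

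**4. Effect seen only at 6 months (r = 0.5).** The pooled estimate averages (0 + 24.7)/2 = 12.35 points (simulated 12.4). Its power is 54%, against 91% for the 6-month contrast. With follow-up rows only, the interaction is significant in 81% of these trials and so leads to within-arm trends; the rest go to the diluted pooled comparison.

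**5. Power of the named 6-month contrast, baseline as covariate.** SE = 31.2 × √(1 − r²) × √(2/26), on 49 df. The critical |t| is 2.01 unadjusted, 2.66 if Tukey covers the four follow-up group-by-time cells, and 2.97 if it covers all six cells.

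| r | SE | d/SE | Unadjusted | Tukey, 4 cells | Tukey, 6 cells |
|---|---|---|---|---|---|
| 0.3 | 8.25 | 2.99 | 83% | 63% | 52% |
| 0.5 | 7.49 | 3.30 | 90% | 74% | 63% |
| 0.7 | 6.18 | 4.00 | 97% | 90% | 84% |

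Unadjusted, 26 per arm is enough. The sample size paragraph allows for no Tukey penalty.

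**The case against.** The strongest reply is that baseline was meant only as a covariate. The text never calls it a response row, and the sentence about combining 3- and 6-month data fits that reading. The interaction would then ask the intended question, and step 2 would fall away. With an equal effect, the pooled comparison would even be powerful (97% or more in simulation). This has force, but the plan does not state that reading, and it cures only the first problem. A significant interaction would still lead to within-arm trends, a non-significant one would still pool, and step 4 shows the cost when the effect develops late.

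It can also be said that the outcome and time point are named, the trial is sized on them, and following an interaction with stratified trends does not forbid a between-group contrast. That is true, but permitting a contrast is not the same as pre-specifying it.

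Three limits on the numbers stand:

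- The 7-12% applies only if a significant interaction is counted as success, which the plan does not say. Its upper end is partly small-sample bias in robust SEs.
- The Tukey families in step 5 are possible readings, not stated ones.
- The normal model is illustrative. On a 0-100 scale a mean of 3.7 allows an SD of at most √(3.7 × 96.3) = 18.9, below the planned 31.2.

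**Conclusion.** The concern holds: the analysis is wrong as written and should be fixed. Two facts rest on the text alone. Baseline is listed both as a time point and as an adjustment, and no branch delivers the 6-month between-group comparison that the plan makes primary and uses for its sample size.

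The size of the problem depends on the assumptions. If baseline rows are responses and the full planned effect is equal at both visits, roughly two thirds to nearly all trials would end in within-arm trends, depending on r. If baseline is a covariate only, that figure does not apply, but the missing primary contrast remains. The stated sample size of 26 per arm is not in error.

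**What to change.** Replace the model description in Section E with text to this effect:

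- The responses are the 3- and 6-month values. The terms are group, time (3 versus 6 months), group-by-time, and the baseline value as covariate only. Keeping baseline as a response, with the arms constrained equal there and no baseline covariate, is equally valid.
- The single primary test is active minus sham at 6 months from this model, two-sided at 0.05, reported whatever the interaction shows and outside the Tukey adjustment.
- Within-arm trends and the pooled 3- and 6-month comparison are supportive description.
- The pairs covered by Tukey's method and the working correlation are named.

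Use the same structure for AF duration, HRV and cytokines. The cost is SAP wording and model code: no new data and no change in sample size.
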